Within this study, HFASD participants assigned to the experimental group will wear the silver plated stainless steel *ProFoveate™* pellets strategically placed on their ears and held in place by the adhesive tape continuously for four weeks.

Study Treatment Instructions

Parents of children assigned to the experimental group will be given instructions on how to use the *ProFoveate™* pellets. The follow instructions will be included on a brochure (See supporting materials) and given to parents of children in the experimental group during visit 2:

TITLE: The Effects of *ProFoveate™* on Reducing Self- Stimulating Behaviors In Children Diagnosed With Autism Spectrum Disorders.

PI: [name]

Co-I: [name]

- 1) The *ProFoveate™* pellets are to be placed on the occiput of the right ear as indicated in the picture below.
- 2) Generally, the *ProFoveate™* pellets should be changed every 2 to 3 days or when they fall off.
- 3) Before applying, the skin should be thoroughly cleaned with alcohol and the tape applied with a good seal.
- 4) Check regularly to ensure that the pellets are in place.
- 5) Write down the date on the *Patient Diary Sheet* each time the pellets are checked.
- 6) You will be supplied with a packet of 50 pellets to use as needed during the 28 days of *ProFoveate™* intervention. All unused pellet are to be returned during the last visit.

Parents and children will be shown exactly where to place the pellets on the ear. Specifically, the Occiput point will be identified for each participant. In traditional Chinese medicine, the Occiput point on the ear may be used to influence brain and spinal cord function. Note in particular the proximity of the vestibular nerve (yellow) to the skin anterior to the ear canal and medial to the pinna on the ear in Figure 2 below. The Occiput point we want to use is behind the ear and lateral to a projection of the vestibular nerve (Figure 3).

[figure not shown]

Figure 2. http://images.emedicinehealth.com/images/eMedicineHealth/illustrations/ear_cutaway.jpg

[figure not shown]

Figure 3: Occiput point on ear.

Study Treatment Compliance

Parents will be provided with a Patient Diary Sheet (see supporting documents) and will be instructed to perform and document daily checks for placement of the pellets.

TITLE: The Effects of *ProFoveate*™ on Reducing Self- Stimulating Behaviors In Children Diagnosed With Autism Spectrum Disorders.
PI: [name]
Co-I: [name]

Device Dispensing and Disposition

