
Parents of each participant in the experimental group will be given a one month supply of silver plated stainless steel pellets (50 pellets) following group assignment at the initial study visit. Used pellets (those removed each time the pellets are changed) will be discarded. Unused pellets will be returned at the final study visit.

Study Design and Procedures

Schedule of Time and Events

Study Procedures	Visit 1	Visit 2	Study Intervention (or no-treatment control) Period	Visit 3	Visit 4
	Day 1	Day 2	Days 2-29	Day 30-34	Day 30-34
Informed Consent	x				
Hearing Screening	x				
TONI-4	x				
Randomization	x				
SSIS – Student Form	x			x	
TOPL-2	x			x	
Parent Questionnaire	x			x	
SSIS – Parent Form	x			x	
Video Taping	x			x	
EEG		x			x
Dispense Test Article ^a		x			
Log in returned Test Article ^a					x
Study Treatment ^a		x	x		
Treatment Compliance ^a		x	x		
Adverse Event Review		x			x

EEG = electroencephalography; TONI-4 = Test of Nonverbal Intelligence 4; SSIS = Social Skills Improvement System; TOPL-2 = Test of Pragmatic Language -2

^aOnly for those subjects assigned to the experimental group

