1 will involve the initial assessments and visit 2 will involve the initial EEG. Visit 3 will involve final assessments and visit Child participants will be assessed using the following measures: 1) hearing screening at 25 decibels for the frequencies 1000, 2000 and 4000 hertz; 2) *Test of Nonverbal Intelligence* 3 (TONI-3; Brown, Sherbenou & Johnsen, 2009; 3) *Social Skills Improvement System SSIS* - Student form (Gresham & Elliot, 2008); and 4) *Test of Pragmatic Language* -2 (TOPL-2; Phelps-Terasaki & Phelps-Gunn, 2007; See Supporting Materials). All assessment procedures with each child in Visits 1 and 3 will be video recorded and analyzed using the observation of self-stimulating behaviors checklist (See Supporting Materials). Additionally, parent participants included in the study will assess their children using a standardize measure: 1) the *Social Skills Improvement System SSIS* - Parent form (Gresham & Elliot, 2008) and a non-standardized measure: 2) the *Questionnaire for Parents of Children with Autism Spectrum Disorders* ([name], 2013) (developed by the researcher to identify self-stimulating behaviors); to assess their children's social skills (See Supporting Materials). Both assessments will be administered at the beginning and end of the study. These assessments are expected to last 2 hours. The twenty-five self-stimulating behaviors identified as a concern for this study include: hand flapping, pulling or twisting ear, scratching, masturbating, shuffling or tapping feet, chewing clothes, picking or rubbing clothes, sucking finger, playing with hair, vocal noises, mouthing, self-injurious behaviors, head banging , rhythmic rocking, twirling objects, tongue rolling and clicking, teeth clicking, head shaking, knocking knees together, gazing at a particular object, repetitive rubbing of mouth and face, finger manipulations, locking hands behind head, grimacing , and tensing whole body and shaking.

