
pressing task that provides the accuracy of their responses and reaction time. Following EEG recordings, ERP analysis time windows will be set *post hoc* permitting a -100 ms pre-stimulus baseline and a post-stimulus time that extends well beyond the P300 latency (e.g., epoch of -100 to 700 ms). EEGs will undergo ocular artifact rejection and be baseline corrected prior to production of an average to all target stimuli. P300 amplitude and latency measures will also be taken. These procedures are expected to last no more than one to one and a half hours in a single session or a split session depending on the needs of the participant. During the administration of ERP procedure, the PI will not be aware if the child participant undergoing the procedure is in the control group or experimental group. This approach will support internal validity and minimize the potential for investigator bias. Sample waveforms showing several ERP components, including [P300](#) are presented in Figures 4.

[figure not shown]

Figure 4: <http://en.wikipedia.org/wiki/File:ComponentsofERP.svg>

Following initial assessment, child participants will be randomly assigned to either the control group (15 participants) or the experimental group (15 participants). Participants in the experimental group will be required to wear the *ProFoveate*™ metal pellets held in place by small adhesive bandages strategically placed on their ears during days 2-29. Participants in the experimental will be told to return for the final assessment on days 30-34 following cessation of treatment. Participants in the control group will receive no study intervention. Participants in the control group will be told to return for final assessment on days 30-34 following initial assessment.

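### Randomisation is scheduled a day before the baseline EEG; randomising after that EEG and before any pellet step would close an avoidable route to bias in the baseline recording

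*Protocol*

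**What the plan says.** **Order of events.** The table under Schedule of Time and Events marks randomisation at Visit 1 (Day 1). It marks EEG at Visit 2 (Day 2) and Visit 4 (Days 30-34). Study Design and Procedures gives Visit 1 to the initial assessments and adds that "visit 2 will involve the initial EEG". Later in that section: "Following initial assessment, child participants will be randomly assigned to either the control group (15 participants) or the experimental group (15 participants".

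**Pellet steps at the EEG visits.** The table footnote restricts the pellet rows to "for those subjects assigned to the experimental group". Dispensing, start of treatment and compliance are marked at Visit 2. "Log in returned Test Article" is marked at Visit 4. Under Study Treatment Instructions, the brochure is "given to parents of children in the experimental group during visit 2". Device Dispensing and Disposition says that pellets are supplied "following group assignment at the initial study visit".

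**Blinding.** During the ERP procedure, "the PI will not be aware if the child participant undergoing the procedure is in the control group or experimental group". The protocol presents this as its guard against investigator bias. The Statistical Plan lists seven dependent variables and calls three of them blinded: P50, P300 and the video ratings. It says that scores will be triangulated because parents are not blinded when they rate.

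**The concern.** The control group receives no treatment, so families know their group once they are told it or handed pellets. Against that background the protocol leans on the blinded measures, and two of the three come from the EEG. The baseline ERP is the reference for any change under research question 3.

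Under the current schedule, allocation already exists when that reference is recorded, and the recording shares a visit with steps that only one group receives. There are two possible routes to bias:

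- **Through the family.** The ERP tasks need sustained attention and button pressing. A child who knows the allocation may engage differently, and blinding the PI does not prevent that.
- **Through the operator.** The operator could see or hear of dispensing or teaching. If a patch were already on, it would sit behind the right ear, near the mastoid where an electrode is taped.

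Neither route need exist at baseline.

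**Working it through.** The protocol states no figure for this point beyond the group sizes, so the check is a count plus a comparison of passages.

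**1. Number of baseline EEGs.** The text plans 15 control and 15 experimental children: 15 + 15 = 30. This agrees with the target of 30 stated in the same section.

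**2. Order of allocation and baseline EEG.** The table gives Day 1 for randomisation and Day 2 for the EEG: 2 - 1 = 1 day. Three further passages bear on this:

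- The visit description keeps the initial assessments (Visit 1) apart from the initial EEG (Visit 2). Read that way, the randomisation sentence agrees with the table.
- The dispensing sentence can attach the initial visit either to the group assignment or to the dispensing. On both readings, assignment happens no later than that visit.
- The design paragraph counts neural activity among the baseline assessments, and the randomisation sentence comes straight after the ERP description. On that reading, randomisation could follow the EEG, and the text would then disagree with the table.

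The first reading is better supported, but the text is not free of doubt. On the table's order, 30 of 30 baseline EEGs follow allocation.

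**3. Order within Visit 2.** The design paragraph describes baseline assessment, then intervention, then reassessment. That implies that the baseline EEG comes before first wear. No passage places it before dispensing or teaching.

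**4. Experimental-only clinic steps by visit.** Visit 1: none. Visit 2: dispensing, teaching and first wear. Visit 3: none. Visit 4: pellet return. They occur at 2 visits, and both are EEG visits.

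**5. Final EEG.** Wear ends on Day 29 and the final EEG is on Days 30-34, that is, 30 - 29 = 1 to 34 - 29 = 5 days later. Pellets should be off by then, which partly protects that recording.

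**6. Effect of moving randomisation.** Baseline EEGs recorded after allocation exists go from 30 of 30 to 0 of 30. Final EEGs recorded after allocation stay at 30 of 30.

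**7. File labels.** Confidentiality gives each child a number from 1 to 15 and a group. For 30 children, 30 / 15 = 2 children share each number if the range is used in both groups, so the number would be unique only with the group attached. The protocol does not say how ERP files are labelled.

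**The case against.** Several objections have force, and they set the limits of the point.

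- **The blind is stated.** A reader might infer from the visit order that the blind is broken or that the protocol contradicts itself on blinding. It does not. The PI's unawareness of group is stated expressly, and the conflict-of-interest management plan and supporting materials, which may add safeguards, are not shown.
- **Existing is not the same as known.** A reader might take 30 of 30 to mean that every baseline EEG is recorded with the group known. No passage says that families or operators are told on Day 1. The count covers allocation that exists, not allocation that has been disclosed.
- **The baseline need not be on treatment.** A reader might infer that pellets could be worn during the baseline EEG. The sequence in the design paragraph points the other way. Only the order of dispensing and teaching is left open.
- **Recording is not scoring.** A reader might conclude that moving randomisation makes the baseline ERP blind without further safeguard. It does not. Analysis windows are set after recording, followed by artifact rejection and measurement of P300, and all of this can take place after allocation. The Statistical Plan calls the measures blinded, so scoring also needs protection.
- **The final EEG remains exposed.** Families know their group by Visit 4 whenever randomisation takes place. The protocol also does not say who dispenses or logs pellets, so a PI who learned the group at Visit 2 could carry it to Visit 4. Reordering reduces this exposure only in part.

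What remains is the order of events at baseline, which can be changed at almost no cost.

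**Conclusion.** The point holds as a cheap design improvement, with moderate confidence. As scheduled, all 30 planned baseline ERPs are recorded one day after allocation, at a visit shared with experimental-only steps whose order relative to the EEG is not fixed. Randomising after the EEG brings the 30 to 0.

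This rests on reading the schedule table together with the visit description. If the randomisation sentence was meant to include the EEG in the initial assessment, the table is wrong and the same edit resolves the mismatch. Neither a failed blind nor disclosure of allocation on Day 1 has been shown. The size of any bias cannot be estimated from the protocol, and the gain is confined to the baseline recording.

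**What to change.** 1. In the Schedule of Time and Events and in the randomisation sentence of Study Design and Procedures, move randomisation to Visit 2, after the baseline EEG is complete and before any dispensing, teaching or first wear. Reword the sentence in Device Dispensing and Disposition to agree.
2. At Visit 4, do the pellet log-in and the adverse event review after the EEG recording.
3. State that all ERPs, baseline and final, are scored blind to group. Label the ERP files with group-neutral numbers 1 to 30 in place of a number from 1 to 15 plus group.

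**Cost.** These are edits to one table and a few sentences, with no added visit or procedure. The practical burden is coordination on Day 2, because allocation must be done between the EEG and dispensing. The protocol also allows a split EEG session. Days 2-29 give 29 - 2 + 1 = 28 days, matching "a packet of 50 pellets to use as needed during the 28 days". If, for example, the second part of a split session fell on Day 3 and wear waited for it, Days 3-29 would give 29 - 3 + 1 = 27 days. The passages on the wear window in Study Treatment Instructions and Study Design and Procedures would then have to be reconciled.

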primary nystagmus response and significantly fewer beats during the secondary response than normal children when stimulated with constant angular acceleration in complete darkness. The greater length of time shows the resistance to nystagmus in this group. It is believed that enhanced stimulation of the Occiput point, which is best accessed behind the ear, could reduce self-stimulating behaviors in children with autism and increase a sense of calm more conducive to learning and social interaction. Roussi, et. al., (2011) demonstrated the importance of electrophysiological measures in making a diagnosis in patients with congenital nystagmus. Congenital nystagmus is an ocular oscillation that usually appears in early infancy. It is most often, but not always, seen in association with visuosensory abnormalities (Gelbart & Hoyt, 1998). *ProFoveate™* has provided the visual acuity often sought through surgery in patients diagnosed with congenital nystagmus. The potential use of this product in patients with autism has not been explored to date. There is some evidence in the literature to suggest that vestibular stimulation may have an impact on behavior and neural activity in children with ASD (Grandin, 1996; Ornitz et.al., 1985; Ornitz, Guthrie & Farley, 1977; Ornitz, Brown, Mason & Putnam, 1974; Miller, Reisman, McIntosh, & Simon, 2001; Ray, King & Grandin, 1988). However, this study represents a unique application of the *ProFoveate™* pellets and has the potential to help individuals with ASD manage self-stimulating behaviors like hand flapping, eye blinking, rocking, staring, etc., which can be deterrents to social interaction.

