Risks include the fact that the adhesives used to hold on the pellets contain trace amounts of latex. If the pellet causes the development of an abrasion, the skin should be allowed to rest 24 hours after which the pellet should be positioned at alternate positions such as shen men or point zero or P6 WRIST position. If the pellets are ingested, drink plenty of fluids and the pellets will be expelled from the body naturally.

Risks Associated with ERP Recordings

Risks associated with ERP recordings are minimal and pose no greater risk to individuals than would occur in daily life. All electronic instrumentation is appropriately grounded, all auditory stimuli are calibrated to safe auditory presentation levels, and all metal surface electrodes are cold sterilized. In the PI's clinical experience, only 1 patient in the 6 years the lab has been in existence experienced a small rash related to a reaction from the medical grade tape we use to secure the electrodes to the face. No other adverse reactions have been reported to any other products we use to prepare the skin surface for the electrodes, and the securing of electrodes to the head. Having to wear electrodes with wires hanging off the head may be disconcerting to some, but we have never experienced early termination of an ERP test because of electrode-related discomfort. Finally, having to sit and actively attend to the visual or auditory stimuli may be uncomfortable to some, but we have never experienced early termination of an ERP test because of discomfort related to our standard procedures.

Other Study Risks

It is possible that a breach of subjects' confidential information could occur. Measures will be implemented to minimize this risk as described in the Data Handling and Recordkeeping section below.

Potential Benefits

The potential benefits to science and humanity that may result from this study include the possibility of finding a treatment procedure for reducing self-stimulating behaviors in children with ASD. This study will provide information to researchers and professionals working with children diagnosed with high functioning autism to help them manage self-stimulating behaviors in this population.

Safety Assessments

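### The abrasion rule moves the pellet to an open list of other points, including the wrist, with no stated return to the Occiput point under study

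*Protocol*

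**What the plan says.** The regimen names one site. The first parent instruction (Protocol, Study Treatment Instructions) says the pellets "are to be placed on the occiput of the right ear". The device section (Test Article, Investigational Device) has them "strategically placed on their ears and held in place by the adhesive tape continuously for four weeks". Study Design and Procedures repeats that they are "held in place by small adhesive bandages strategically placed on their ears during days 2-29".

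The rationale is specific to the same site. The background section states the belief that "enhanced stimulation of the Occiput point, which is best accessed behind the ear, could reduce self-stimulating behaviors" in children with autism. Study Treatment Instructions adds: "The Occiput point we want to use is behind the ear and lateral to a projection of the vestibular nerve". The device section says the five-pellet patch was chosen so that placement on the occiput would be reliable in children.

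Risks Associated with ProFoveate then gives the rule for an abrasion: 24 hours of rest for the skin, "after which the pellet should be positioned at alternate positions such as shen men or point zero or P6 WRIST position". It sets no limit on how long the alternate site is used and does not mention going back.

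**The concern.** The abrasion rule does more than protect the skin. It directs continued treatment somewhere else, at a site chosen from examples. One of those examples is not on the ear, and the protocol gives no reason to expect the studied effect there. A family following the rule literally would stop delivering the intervention that the trial sets out to test and start a different one, with no instruction to go back.

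What is at stake is exposure. The experimental arm has 15 children. If some wear the pellet mainly at other points, the arm's result reflects a mixture of sites, and a weak or absent effect at the Occiput becomes harder to interpret. Where the device is worn and what is done after a skin injury are protocol content, so this is not a detail that can wait for an analysis plan.

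**Working it through.** The protocol gives no figure on this point to reproduce. The check is a comparison of text, followed by simple proportions for scale.

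**Text comparison**

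| Feature | Regimen and rationale | Abrasion rule |
|---|---|---|
| Site | Occiput of the right ear | Alternate points, given as examples |
| Body area | On the ears | Includes the wrist |
| Continuity | Continuous for four weeks | 24-hour rest, then another site |
| Return to the Occiput | Not applicable | Not stated |

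The wrist is the firmest mismatch. The documents do not say where the other two named points lie, so nothing here depends on whether they are ear points. Either way they are alternatives to the Occiput. No other section closes the list or states a return, and the regimen sections mention no exception.

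**Inputs**

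- Treatment period: days 2-29, so 29 - 2 + 1 = 28 days (Study Design and Procedures).
- Experimental arm: 15 children (same section).
- Patch change: every 2 to 3 days (Study Treatment Instructions).
- Abrasion rate: not given.
- Day of abrasion, d days of wear: 2-3 is the first patch change; 14 and 21 are illustrations.
- Healing time: not given; 3-7 days is assumed below.

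**Weight of one child:** 1/15 = 6.7% of the arm. Planned exposure is 15 x 28 = 420 child-days.

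**The rest day alone:** 1/28 = 3.6% of one child's period.

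**Worst case, no return.** Share of the child's period off the Occiput = (28 - d)/28. Share of the arm's exposure = (28 - d)/420. Both count the rest day.

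| d | Days off | Share of child's period | Share of arm's exposure |
|---|---|---|---|
| 2 | 26 | 92.9% | 6.2% |
| 3 | 25 | 89.3% | 6.0% |
| 14 | 14 | 50.0% | 3.3% |
| 21 | 7 | 25.0% | 1.7% |

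**Part attributable to the wording.** A rule that waits for healing also loses the healing days. With healing time h of 3-7 days, the avoidable loss is 28 - d - h:

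- d = 2: 19-23 days, or 19/420 = 4.5% to 23/420 = 5.5% of the arm's exposure.
- d = 14: 7-11 days, or 1.7% to 2.6%.
- d = 21: 0-4 days, or 0% to 1.0%.

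These are per affected child. No number of affected children is assumed.

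**The case against.** The rule is a conditional safety instruction in the risk section. A general regimen and an exception for injury can coexist, and moving a pellet off broken skin is right. The device section also describes the product in general terms as worn about the face and ears, so another ear or face point is not wholly foreign to it. An off-ear site even has a merit: it spares irritated ear skin. All of this stands, and it reduces the point to how the exception is drafted. It does not supply a closed list, a return, or a reason to expect the studied effect at the wrist.

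Silence about a return is also not an instruction never to return. The first parent instruction remains the standing regimen and patches are changed every few days, so a family might well resume at the Occiput after healing. This stands too, which is why the 89-93% is an upper limit under one reading and not an expected loss.

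A reader might go further in two ways that the documents do not support:

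- **That the rule contradicts the days 2-29 window.** A change of site does not alter the window. The final assessment still falls when participants "will be told to return for the final assessment on days 30-34 following cessation of treatment". Only the 24-hour rest interrupts continuous wear.
- **That families are left without safety guidance at home.** No visit is scheduled between Day 2 and Days 30-34, the six listed instructions have no abrasion step, and the diary entry they request is the date "each time the pellets are checked". But the brochure and diary are not shown and may say more. Study Treatment Compliance has parents document daily checks of placement, which might capture a changed site. No gap is established.

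**Conclusion.** The point holds as a minor one and a cheap improvement. The abrasion rule has three drafting faults: an open list of sites, a wrist site outside the on-ear regimen, and no stated return to the Occiput. Followed literally, it substitutes a different treatment for an injured child where a pause in the studied one would suffice.

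The effect is diluted exposure at the Occiput for any relocated child, each 6.7% of the experimental arm. The total size is unknown, because it depends on an abrasion rate that the protocol does not give and that may be zero. The worst-case percentages assume no return and include healing time; the narrower figures rest on the assumed 3-7 days of healing.

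A reader might infer that the trial's comparison is compromised. It is not: the randomised groups stand, and under Safety Assessments an abrasion would be recorded as an adverse event. This is also a pilot study.

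**What to change.** In Risks Associated with ProFoveate, replace the open list with a rule to rest the skin until healed and then resume at the Occiput of the right ear. If treatment during healing is wanted, allow one named temporary fallback site on the ear. Remove the wrist site.

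Put the same step in the parent instructions and, if a fallback is kept, show it to families at Visit 2. Record the site and dates of any rest or relocation, if the diary does not already do so. Keep the child in the randomised group with Visits 3 and 4 as scheduled.

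The cost is a sentence in the protocol, a line in the parent instructions, perhaps one diary column, and an IRB amendment. The downside is slightly more recording by parents and a few days without the pellet, or at the fallback site, while the skin heals. Dropping the wrist also gives up a site that would spare the ear entirely; a pause until healing serves that purpose.
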